### **5.4.1 Prohibited Medications and Therapy**

Concomitant administration of the following types of drugs and procedures is not allowed:

- Recently completed drug-drug interaction study showed a mild (approximately 40%) increase of AUC of HBI-8000 when itraconazole, a strong CYP3A4, was administered concurrently. The use of potent CYP3A4 inducers or inhibitors ([Appendix 3](#)) should be avoided.
- Live vaccines within 30 days prior to the first dose of trial treatment and while participating in the trial. Examples of live vaccines include, but are not limited to, the following: measles, mumps, rubella, chicken pox, yellow fever, seasonal flu (that contain a live virus), H1N1 flu, rabies, BCG, and typhoid vaccine.
- Surgery for tumor control or symptoms management is not permitted during the study.
- Concomitant administration of anti-tumor treatment other than the Study Treatment, or procedures that could interfere with the evaluation of safety or anti-tumor effect of Study Treatment, is prohibited during the study.

### **5.4.2 Supportive Care and Other Medications**

Systemic use of corticosteroids at doses  $\leq$ 10 mg/day of prednisolone, or converted equivalent dose, is permitted during the study. Brief use of higher dose of prednisone or its equivalent is also permitted to manage immune related toxicities as indicated. Supportive care to mitigate toxicities such as anti-emetics for nausea, and granulocyte-colony stimulating factor (G-CSF) for neutropenia are also allowed.

Palliative and supportive care is permitted during the course of the trial for underlying medical conditions and management of symptoms.

Palliative radiation therapy (limited field) is permitted only for pain control if considered medically necessary by the treating physician as long as the lesion is NOT a RECIST 1.1 defined target lesion and is NOT administered for tumor control. Study treatment should be held during the course of palliative radiotherapy and should be resumed no earlier than the next scheduled administration of study treatment. The specifics of the radiation treatment, including the location,

will be recorded. The Sponsor Medical Monitor must be consulted prior to initiating any radiation therapy.

In order to provide optimal patient care, and to account for individual medical conditions, the Investigator may apply discretion to prescribe supportive care (e.g., acetaminophen, diphenhydramine, antimicrobials) according to local institutional guidelines. After the first cycle, pre-medication for anticipated adverse events may also be provided, according to local institutional guidelines.

Subjects must be instructed to first consult with their study doctor before taking any additional medications (including over-the-counter or prescription medications and supplements including those prescribed/recommended by other physicians/dentists) during the study.

#### **5.4.3      Restricted Medications**

- Antiarrhythmic drugs such as amiodarone, disopyramide, procainamide, etc., and other drugs known to prolong the QT interval such as clarithromycin, moxifloxacin, bepridil, etc., may increase QT interval prolongation, and their coadministration should therefore be avoided. If such a drug is going to be co-administered, the patient's condition should be monitored closely.
- Bisphosphonates and/or RANKL inhibitor therapies used to prevent bone resorption, cannot be initiated after informed consent has been signed. These therapies may be continued IF treatment with an agent from one of these two classes was initiated PRIOR to signing informed consent.
- COVID-19 vaccination should be administered >7 days before Cycle 1 Day 1.

#### **5.5      Food Effects**

The study evaluating the effect of food on oral bioavailability of HBI-8000 has shown comparable drug exposure of HBI-8000 tablets when taken under fasting or fed conditions. In this study, HBI-8000 should be taken approximately 30 minutes after a meal.

Due to potential food-drug interactions, grapefruit, grapefruit juice, Seville oranges, and any products that contain Seville oranges or grapefruit should be avoided within 7 days prior to C1D1 through 7 days after the last dose of HBI-8000.

#### **5.6      Dose Modification**

##### **5.6.1      HBI-8000 Administration**

Subjects will take 30 mg of Study Treatment orally approximately 30 minutes after a meal, beginning on Day 1 and continue every 3 to 4 days on the BIW schedule without interruption (e.g., Monday and Thursday, or Monday and Friday repeating every week).

##### **5.6.1.1      HBI-8000 Dose Reduction**

Once HBI-8000 dose is reduced, it will not be increased. This dose reduction guideline applies to the entire study duration.

If a subject experiences any of the toxicities described below, the dose of HBI-8000 will be reduced. One dose reduction (30 mg to 20 mg) is allowed for non-hematological toxicities, and two dose reductions (30 mg to 20 mg and 20 mg to 10 mg) are allowed for hematological toxicities. Dose reduction for other toxicities not described below may be possible after approval from the sponsor.

**A. Hepatic Non-Hematologic Toxicity**

- Isolated Grade 4 AST/ALT
- Isolated Grade 3 AST/ALT that fails to return to Grade 1 or less within 5 days
- Isolated total bilirubin  $\geq$ Grade 3
- AST or ALT  $>3 \times$  ULN AND concurrent total bilirubin  $>2 \times$  ULN

**B. Non-Hepatic Non-Hematological Toxicity**

Any Grade 3 or greater non-hepatic non-hematologic toxicity except for the following:

- Grade 3 electrolyte abnormalities that are not complicated by associated clinical adverse experiences, last less than 48 hours and either resolve spontaneously or respond to conventional medical intervention.
- Grade 3 nausea or vomiting that lasts less than 48 hours, and either resolves spontaneously or responds to conventional medical intervention.
- Isolated Grade 3 elevation of amylase or lipase not associated with clinical or radiographic evidence of pancreatitis.
- Isolated Grade 3 fever that lasts  $\leq 3$  days and is not associated with hemodynamic compromise (i.e., hypotension, clinical or laboratory evidence of impaired end-organ perfusion).

**C. Immune-related AEs (irAE)**

- Any Grade 2 or greater eye pain or reduction in visual acuity that does not respond to topical therapy and does not improve to Grade 1 severity within 2 weeks of the initiation of topical therapy or any Grade 2 or greater eye pain or reduction in visual acuity that requires systemic treatment.
- Any other Grade 3 or greater irAE

If pembrolizumab is withheld or permanently discontinued due to an immune-mediated reaction, HBI-8000 should be withheld or permanently discontinued, respectively.

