### **4.5 Discontinuation of Investigational Product and Participant Withdrawal**

Subjects discontinued from HBI-8000 for toxicity in the absence of disease progression may continue to receive pembrolizumab under standard of care and be followed for disease response as long as consent to study participation remains effective. Similarly, if pembrolizumab administration is discontinued due to unacceptable toxicities (other than immune-mediated reactions) associated with pembrolizumab, the subject may continue to receive HBI-8000, at the Investigator's discretion in consultation with Sponsor Medical Monitor and be followed for disease response as long as consent to study participation remains effective. When both HBI-8000 and pembrolizumab have been discontinued and disease has not progressed, the subject will continue to be followed for disease status in the Follow-up Phase until evidence of progression.

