**D. Hematologic Toxicity**

- Grade 4 neutropenia  $\geq 7$  days in duration
- Grade 4 thrombocytopenia, or any Grade 3 thrombocytopenia associated with clinically significant bleeding

- Grade  $\geq 3$  febrile neutropenia
- Grade  $\geq 3$  hemolysis

HBI-8000 treatment will resume at a reduced dose only after toxicity has returned to Grade  $\leq 1$  within 14 days from the occurrence of the toxicity. For neutropenia, the use of G-CSF should be considered. If the same toxicity recurs despite allowed dose reduction(s), HBI-8000 will be discontinued. If toxicity is not related to pembrolizumab, at Investigator's discretion a subject may continue to receive pembrolizumab while remaining in study Follow-Up.

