### **5.6.1.2 HBI-8000 Dose Delay Independent of Pembrolizumab Administration**

At the Investigator's discretion, the dose of HBI-8000 may also be delayed for up to 14 days from the scheduled time of dosing, for any toxicity possibly or probably related to HBI-8000 that does not meet toxicity criteria described in Section 5.6.1.1. In the event of Grade 3 uncomplicated thrombocytopenia or neutropenia HBI-8000 dosing should be held until recovery to Grade  $\leq 1$  before resuming again. Supportive care with hematological growth factors may be prescribed at the discretion of the Investigator.

Dosing may be interrupted to assess or treat intercurrent illnesses. The Sponsor's representative should be notified of any treatment interruption. In the event of interruption of  $>14$  days, resumption of dosing should be discussed with Sponsor to assess potential benefit for continuation of HBI-8000.

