### **5.6.2.1.2 Pembrolizumab Dose Delay Independent of HBI-8000 Administration**

Investigators should withhold a dose as described in the KEYTRUDA USPI (Recommended treatment modifications) until it is reduced to a Grade 1 or resolved. Once resolved, the dose may be reinstated. For subjects who were treated with steroids for irAE, steroids need to be tapered to

a dose 10 mg or less of prednisone or equivalent over at least 1 month before resuming pembrolizumab. The administration of HBI-8000 may continue as scheduled during pembrolizumab dosing interruption.

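### Section 5.6.2.1.2 lets HBI-8000 continue during a temporary pembrolizumab hold for an immune-related event, where Section 5.6.1.1 C says it should be withheld

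*Combined protocol and SAP*

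**What the plan says.** Two sections tell a site what to do with HBI-8000 when pembrolizumab is held.

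- Section 5.6.1.1 C (immune-related AEs): "If pembrolizumab is withheld or permanently discontinued due to an immune-mediated reaction, HBI-8000 should be withheld or permanently discontinued, respectively".
- Section 5.6.2.1.2 (pembrolizumab dose delay): a hold follows the US package insert and lasts until the event has fallen to Grade 1 or cleared. Then comes "For subjects who were treated with steroids for irAE, steroids need to be tapered to" 10 mg of prednisone or less, over at least one month, before pembrolizumab resumes. The next sentence is: "The administration of HBI-8000 may continue as scheduled during pembrolizumab dosing interruption".

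The surrounding rules are these.

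- Section 5.6.1.1: "If a subject experiences any of the toxicities described below, the dose of HBI-8000 will be reduced". For irAEs the triggers are certain eye events of Grade 2 or higher and "Any other Grade 3 or greater irAE".
- End of Section 5.6.1.1, printed under D (hematologic toxicity): "HBI-8000 treatment will resume at a reduced dose only after toxicity has returned to Grade" 1 or lower, within 14 days.
- Section 5.6.1.2: the investigator may delay HBI-8000 for up to 14 days for lesser toxicity possibly or probably related to it. After an interruption of more than 14 days, "resumption of dosing should be discussed with Sponsor to assess potential benefit for continuation of HBI-8000".
- Section 4.5 lets HBI-8000 continue after pembrolizumab is stopped for "unacceptable toxicities (other than immune-mediated reactions) associated with pembrolizumab". Section 5.6.2.1.1 makes the same exclusion. Both concern discontinuation only.

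**The concern.** One section says to withhold HBI-8000 when pembrolizumab is held for an immune-mediated reaction; another permits dosing to go on. The permission stands in the section that a site would consult when it delays pembrolizumab, and that section has no cross-reference to 5.6.1.1 C.

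At stake is dosing during active immune toxicity. Section 1.1.3.3 lists pneumonitis and interstitial lung disease among the important identified risks of HBI-8000, and Section 6.2.2.4.6 makes immune-related toxicities the events of special interest. With 6 to 10 sites, two investigators could handle the same event differently and each point to protocol text.

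**Working it through.** The plan gives no figure for this point, so the check is a comparison of the rules case by case, followed by a count of doses.

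**Step 1. Does 5.6.2.1.2 cover immune-related holds?** Yes. The sentence just before the permission sets the steroid taper for irAEs, so these holds are within the section's scope.

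**Step 2. The cases.**

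| Pembrolizumab action for an irAE | What applies to HBI-8000 | Result |
|---|---|---|
| Permanent discontinuation | 5.6.1.1 C: discontinue. 4.5 and 5.6.2.1.1: the permission to continue excludes immune-mediated reactions | Body text agrees |
| Temporary hold, Grade 3 or higher (or a listed eye event) | 5.6.1.1: mandatory dose reduction. 5.6.1.1 C: withhold. 5.6.2.1.2: may continue as scheduled | Largely closed until recovery; a smaller gap remains |
| Temporary hold, below Grade 3 | 5.6.1.1 C: withhold. 5.6.2.1.2: may continue as scheduled. 5.6.1.2: discretionary delay of up to 14 days | Open conflict |

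*Below Grade 3.* The label's thresholds are not reproduced, so the existence of such holds is an inference: a hold that ends when the event drops to Grade 1 implies that some holds begin at Grade 2. Eye events aside, the withhold sentence in 5.6.1.1 C is then the only irAE rule that directs HBI-8000 to stop. The delay in 5.6.1.2 is optional and requires a possible or probable link to HBI-8000.

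*Grade 3 or higher.* If the restart sentence printed under D also applies to irAEs, HBI-8000 may resume at a reduced dose once the event is Grade 1 or lower, while pembrolizumab may stay on hold through a taper of at least one month. In that window 5.6.1.1 C would keep HBI-8000 off and 5.6.2.1.2 would not. If the restart sentence applies to hematologic toxicity only, the protection at Grade 3 or higher is the dose reduction alone, and the gap is wider.

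**Step 3. Doses at issue for one affected subject.** HBI-8000 is given twice a week (Section 5.6.1).

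- 14-day hold: 2 weeks × 2 = 4 doses.
- One-month taper, with HBI-8000 off throughout: 4 weeks × 2 = 8 doses; with a month of 365/12/7 = 4.35 weeks, 8.7 doses. So about 8 to 9.
- With pembrolizumab every 6 weeks, an event and its taper may fall between infusions. If no infusion is withheld, the difference may be nil.

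**Step 4. Knock-on effects of withholding.** Two 3-week cycles hold 2 × 3 × 2 = 12 doses, and 75% of 12 is 9, which reproduces the per-protocol threshold in Section 7.2.

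- A 14-day hold in the first two cycles leaves 12 − 4 = 8 doses, below 9 if the doses are counted over those cycles.
- Section 4.4.1 gives omission of more than one third of the dose over 6 weeks as an example of noncompliance. A 14-day hold is 4/12, exactly one third and so not above it; 8 doses missed is 8/12, well above it.

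**The case against.** The best defence is that the specific rule governs the general one. Section 5.6.1.1 C is directed at immune-mediated reactions and says HBI-8000 should be withheld; 5.6.2.1.2 only says that it may continue. A site that withholds complies with both, and the intent can be recovered from 4.5, 5.6.1.1 C and 5.6.2.1.1. Section 5.6.1.2 adds a discretionary route for many lower-grade events. Section 1.1.3.3 also reports no evidence of more immune-related toxicity with the nivolumab combination than expected from nivolumab alone.

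All of that stands, and it limits the severity. It does not remove the conflict. The permission directly follows the irAE taper rule, so it is hard to read as confined to non-immune holds. The exception is written out for discontinuation and missing for holds. A site that keeps dosing can therefore cite express permission for something 5.6.1.1 C says should not happen.

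Three stronger readings are tempting, and the documents do not support them.

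- *That the body text also conflicts on permanent discontinuation.* It does not; all three sections agree.
- *That HBI-8000 may run on unchanged through severe irAEs.* A reduction is mandatory from Grade 3.
- *That a frequency can be taken from the KEYNOTE 001 results in Section 1.1.1.* Those give immune-mediated events under pembrolizumab alone, not holds by grade, and the hold criteria are not in the documents.

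**Conclusion.** The inconsistency is real and should be fixed. Sections 5.6.1.1 C and 5.6.2.1.2 give conflicting instructions for HBI-8000 during a temporary pembrolizumab hold for an immune-mediated reaction. The conflict is clearest below Grade 3, and a smaller gap remains at Grade 3 or higher.

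How many of the 20 to 24 subjects would meet it is not estimable from the documents. The per-subject difference of 4 doses, or about 8 to 9, assumes twice-weekly dosing and, for the larger figure, that HBI-8000 stays off until the taper ends; 5.6.1.1 C does not say when it restarts. That holds occur below Grade 3 is inferred from the rule for ending a hold.

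A reader might infer that the efficacy results are compromised. The documents do not support that: the full analysis set requires only one HBI-8000 dose given with pembrolizumab (besides eligibility and a post-baseline assessment), so a hold after the first dose does not itself remove a subject. The one analysis consequence shown here is possible loss of an affected subject from the per-protocol set.

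**What to change.** In Section 5.6.2.1.2, keep the sentence "The administration of HBI-8000 may continue as scheduled during pembrolizumab dosing interruption" and add to it: *except when pembrolizumab is withheld for an immune-mediated reaction, in which case HBI-8000 is also withheld (see 5.6.1.1 C).*

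Add when HBI-8000 may restart, for example when pembrolizumab resumes, with any hold of more than 14 days discussed with the Sponsor under 5.6.1.2. The sponsor should also set the restart dose after a hold below Grade 3, and say whether the restart sentence printed under D covers irAEs. State that toxicity holds do not count as noncompliance under 4.4.1.

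Optionally, align the Study Treatment entry of the synopsis, which lets HBI-8000 continue after pembrolizumab-related toxicity without the immune-mediated exception or the Medical Monitor consultation found in 4.5 and 5.6.2.1.1. This is tidying, not a separate safety defect.

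The cost is a short protocol amendment with IRB approval (Section 8.3.6), and no added visits, procedures or subjects. An affected subject may miss some HBI-8000 doses, as 5.6.1.1 C already intends, and an early hold could take that subject below the 9-dose per-protocol threshold.

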**D. Hematologic Toxicity**

- Grade 4 neutropenia  $\geq 7$  days in duration
- Grade 4 thrombocytopenia, or any Grade 3 thrombocytopenia associated with clinically significant bleeding

- Grade  $\geq 3$  febrile neutropenia
- Grade  $\geq 3$  hemolysis

HBI-8000 treatment will resume at a reduced dose only after toxicity has returned to Grade  $\leq 1$  within 14 days from the occurrence of the toxicity. For neutropenia, the use of G-CSF should be considered. If the same toxicity recurs despite allowed dose reduction(s), HBI-8000 will be discontinued. If toxicity is not related to pembrolizumab, at Investigator's discretion a subject may continue to receive pembrolizumab while remaining in study Follow-Up.

### **5.6.1.2 HBI-8000 Dose Delay Independent of Pembrolizumab Administration**

At the Investigator's discretion, the dose of HBI-8000 may also be delayed for up to 14 days from the scheduled time of dosing, for any toxicity possibly or probably related to HBI-8000 that does not meet toxicity criteria described in Section 5.6.1.1. In the event of Grade 3 uncomplicated thrombocytopenia or neutropenia HBI-8000 dosing should be held until recovery to Grade  $\leq 1$  before resuming again. Supportive care with hematological growth factors may be prescribed at the discretion of the Investigator.

Dosing may be interrupted to assess or treat intercurrent illnesses. The Sponsor's representative should be notified of any treatment interruption. In the event of interruption of  $>14$  days, resumption of dosing should be discussed with Sponsor to assess potential benefit for continuation of HBI-8000.

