### 1.1.3.3 HBI-8000 Safety Profile

As a monotherapy, the main safety findings for HBI-8000 are myelosuppression (thrombocytopenia, neutropenia, leukopenia, and anemia) observed in heavily pre-treated relapsed and refractory T-cell lymphoma patients. Additional toxicities included gastrointestinal symptoms, fatigue and asymptomatic laboratory abnormalities. Toxicities were generally mild and manageable with supportive care, dose reductions, interruption, or delays.

In clinical studies, treatment with HBI-8000 has been associated with exposure-related myelosuppression, categorized as important identified risk and includes thrombocytopenia, anemia, and neutropenia or lymphopenia. These myelosuppression related toxicities were more severe in patients with relapsed and refractory hematological malignancies than in patients with solid tumors. In general, the hematologic AEs are manageable with supportive care such as hematological growth factor administration, dosing interruption and dose reduction. Other important identified risks are pneumonitis, interstitial lung disease, and interstitial pneumonia.

In the HBI-8000-302 study, the safety of HBI-8000 administered in combination with standard dose immune checkpoint inhibitor (CPI), nivolumab, has been evaluated in 89 patients total including 49 with melanoma, 29 with NSCLC and 11 with renal cell carcinoma. The most common AEs of all grades associated with HBI-8000 were fatigue (59.6%), thrombocytopenia (49.4%), nausea (48.3%), diarrhea (47.2%), anemia (42.7%), dyspnea (37.1%), peripheral edema (33.7%), anorexia (32.6%), neutropenia (31.5%) and leukopenia (31.6%). The most reported Grade 3 or higher adverse events were lymphopenia, neutropenia, hypophosphatemia, fatigue, anemia and diarrhea. Only 3 subjects had transaminase elevation were reported as Grade 3. The safety profiles so far have been consistent with those observed in HBI-8000 monotherapy, although the hematological toxicities were less severe and less frequent, as expected with solid tumor patient population. There has been no evidence of increased risk for immune-related toxicity over those expected with nivolumab treatment alone.

Arrhythmia including QTc prolongation may occur and are categorized as important potential risk. However, recently, a QT interval corrected by heart rate (QTc) **HBI-8000-302**

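### Afebrile Grade 4 neutropenia lasting under 7 days has no directed dosing action, although Grade 3 neutropenia has a directed hold

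*Combined protocol and SAP*

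**What the plan says.** Five provisions of the protocol bear on a low neutrophil count during HBI-8000 treatment.

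- **Default schedule (Section 5.6.1).** Subjects start on Day 1 and "continue every 3 to 4 days on the BIW schedule without interruption".
- **Reduction triggers (Section 5.6.1.1 D).** The list includes "Grade 4 neutropenia" of 7 days or more and, separately, "febrile neutropenia" of Grade 3 or higher. For platelets the entry is "Grade 4 thrombocytopenia, or any Grade 3 thrombocytopenia associated with clinically significant bleeding", with no duration condition on Grade 4. After a listed toxicity, treatment resumes at a reduced dose once the event is back to Grade 1 or lower within 14 days.
- **Directed hold (Section 5.6.1.2).** "In the event of Grade 3 uncomplicated thrombocytopenia or neutropenia HBI-8000 dosing should be held until recovery to Grade" 1 or lower. Grade 4 is not named.
- **Optional delay (Section 5.6.1.2, preceding sentence).** "At the Investigator's discretion, the dose of HBI-8000 may also be delayed for up to 14 days from the scheduled time of dosing". This covers toxicity possibly or probably related to HBI-8000 that does not meet the Section 5.6.1.1 criteria.
- **Optional reduction (Section 5.6.1.1).** "Dose reduction for other toxicities not described below may be possible after approval from the sponsor".

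On background risk, Section 1.1.3.3 lists myelosuppression as an important identified risk. For the nivolumab combination it reports: "The most reported Grade 3 or higher adverse events were lymphopenia, neutropenia, hypophosphatemia, fatigue, anemia and diarrhea".

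**The concern.** A site that finds an afebrile Grade 4 neutrophil count cannot usually know at that moment how long it will last. Until 7 days have passed, the reduction trigger is not met. The directed hold names Grade 3 only. The site is left with a provision that permits a delay and a schedule that otherwise runs on. A Grade 3 count at the same visit would have carried a direct instruction to hold.

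Two things are at stake. The first is subject safety: some subjects could receive further doses at Grade 4 because the text does not address their case. The second is the tolerability data. Safety and tolerability are a secondary objective (Section 2.2), and Section 7.4.2 reports compliance and relative dose intensity for HBI-8000. If sites handle the same count differently, part of the variation in those summaries reflects site choice rather than the drug.

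**Working it through.** The documents state no figure for this point, so there is none to reproduce. The check has three parts.

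**1. The rules side by side.** I take uncomplicated neutropenia to mean afebrile neutropenia.

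| Neutropenia category | Reduction trigger (5.6.1.1 D) | Directed hold (5.6.1.2) |
|---|---|---|
| Grade 3, afebrile, any duration | No | Yes |
| Grade 4, afebrile, under 7 days | No | No |
| Grade 4, afebrile, 7 days or more | Yes | No |
| Grade 3 or higher, febrile | Yes | No |

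Only the second row has no directed action. The same table for thrombocytopenia has no empty row: every Grade 4 is a trigger, Grade 3 with clinically significant bleeding is a trigger, and uncomplicated Grade 3 is held.

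**2. Doses falling due in the gap.** Section 5.6.1 gives Monday/Thursday or Monday/Friday as examples, so gaps between doses alternate between 3 and 4 days. The longest dose-free run is 3 days, two doses can fall within 4 consecutive days, and three doses need at least 8 days.

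| Length of window | Scheduled doses, minimum to maximum |
|---|---|
| 1 to 3 days | 0 to 1 |
| 4 to 6 days | 1 to 2 |
| 7 days | 2 |

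An episode that stays in the gap therefore spans 0 to 2 scheduled doses. A full 7-day wait always contains 2. Table 1 schedules hematology on Day 1 of each 21-day cycle, and Section 6.3 adds tests as clinically indicated. Even with the ±3-day visit windows, two scheduled counts are at least 21 − 6 = 15 days apart, so no scheduled test settles the 7-day question.

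**3. How many subjects.** Section 1.1.3.3 gives 89 patients in the earlier combination study. Section 1.1.5 lists neutropenia among the events seen at Grade 3 and names only lymphopenia at Grade 4. Assume this means 0 Grade 4 neutropenia in 89 patients.

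- One-sided 95% upper bound: 1 − 0.05^(1/89) = 0.033, or 3.3%.
- Expected subjects at that bound: 20 × 0.033 = 0.7 and 24 × 0.033 = 0.8.
- Chance of at least one at that bound: 1 − 0.05^(20/89) = 49% for 20 subjects and 1 − 0.05^(24/89) = 55% for 24.

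These figures cover all Grade 4 neutropenia. Cases that are febrile or last 7 days or more already have an action, so the count in the gap is smaller.

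**The case against.** The strongest case on the other side is that this is one empty cell, and not an unprotected one. The optional delay was written for toxicities that miss the Section 5.6.1.1 criteria, Section 4.4.1 allows discontinuation for unacceptable toxicity, and Section 6.2.2.4.2 describes Grade 4 as life-threatening. Many investigators would hold without being told. A subject already held at Grade 3 who worsens to Grade 4 stays held until recovery to Grade 1 or lower, and a Grade 4 count that improves to Grade 3 meets the hold. The gap is therefore confined to afebrile neutropenia first found at Grade 4, while it stays there, for under 7 days. All of this stands. It limits the reach of the problem but leaves the more severe category with a permission where the milder one has an instruction.

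A second objection is that Grade 3 in the hold sentence should be read as Grade 3 or higher. The text does not say so, and Section 5.6.1.1 D writes the at-least-Grade-3 form for febrile neutropenia and hemolysis where that is meant.

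Three stronger readings are tempting, and the documents do not support them.

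- A reader might infer that the neutropenia rules are inverted throughout. They are not: prolonged Grade 4 and febrile cases lead to a reduction, which goes further than a hold.
- A reader might take the 31.5% any-grade neutropenia rate in Section 1.1.3.3 (0.315 × 20 = 6.3 to 0.315 × 24 = 7.6 subjects) as the number at risk. That rate says nothing about Grade 4.
- A reader might conclude that hold and reduction rates become uninterpretable. With under 1 expected subject they do not. Worst-grade adverse event tables (Section 7.5.2.1) and laboratory shift tables (Section 7.5.2.2) would show the Grade 4 events, and exposure is reported separately.

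**Conclusion.** The point holds as a gap between two subsections. Afebrile Grade 4 neutropenia under 7 days meets neither the reduction trigger nor the directed hold, so it carries a weaker instruction than Grade 3, and 0 to 2 scheduled doses are left without guidance while duration is established.

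The likely number affected is small: under 1 expected subject in 20 to 24 at the upper bound of 3.3%. That rests on three assumptions: that the narrative in Section 1.1.5 is complete, that it means no Grade 4 neutropenia in 89 patients, and that experience with nivolumab across 20, 30 and 40 mg carries over to 30 mg with pembrolizumab. Section 1.1.5 is prose and not a table, so the zero is an inference.

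The ORR definition and its planned analysis do not depend on this wording. The effect on hold and dose-intensity summaries is modest. The change is worth making because the event is serious, myelosuppression is an identified risk and the correction is cheap.

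**What to change.** Reconcile Sections 5.6.1.1 D and 5.6.1.2, preferably in one hematologic table. Each neutropenia category (Grade 3; Grade 4 under 7 days; Grade 4 of 7 days or more; febrile) should map to one stated action. The table should also say what happens to scheduled doses while the duration of a Grade 4 count is still being established. Which action applies in each row is for the sponsor's clinical team to decide.

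The cost is an amendment to the wording of two subsections. It needs no extra subjects and no added scheduled visits, and may lead to a few more recorded holds.
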